5.3 Recruitment and Screening

(swissethics 3b) [69]

Preschool children with chronic respiratory symptoms will be recruited at the outpatient clinic of our department.

For optimal matching of healthy controls we will give additional flyers to the parents of children with chronic respiratory symptoms to inform the classmates or groupmates of their children. Healthy siblings also can be considered as a healthy control. In case of interest from potential healthy controls additional information will be provided by the study doctor. If sufficient number of healthy controls is not reached, healthy children will be recruited from public schools, day care centers, from the public (the choice of the schools and nurseries as well as children's events for public recruitment will be decided later according to our needs).

Recruitment comprises of the following:

- Patient contact, assessment for inclusion and exclusion criteria
- Informed consent and appointment for breath testing
- University Children's Hospital Zurich (ca. 20-60 min):breath testing

Participants will be reimbursed for travel expenses upon request and can withdraw from the study without giving reasons at any time without their decision impacting in any way on their clinical care. Healthy control persons (≤ 18 years) will be recruited from the general population by printed flyers, newspaper advertisements and personal communication. They will follow the same testing regimen as children with respiratory symptoms. For healthy controls besides the breath test spirometry, exhaled NO measurement and sin-prick test will be performed. Prior to the test appointment a questionnaire will be filled-in by parents to assess the respiratory health status of the healthy controls.

Participants will not be subjected to any invasive or distressing test or intervention procedures beyond skin prick testing. Other than sparing about one hour of their time to travel to and from the University Children's Hospital Zurich, having above mentioned tests done, participants will not experience any additional inconveniences. All investigators and participants are fully informed about the study design and no concealment or group allocation is necessary. All measurements will be undertaken by a small set of trained investigators in a standardised fashion. Participant confidentiality is a priority.

5.4 Methods of minimising bias

(STROBE 9; swissethics 2) [6,69]

Selection bias: to reduce selection bias all patients with respiratory symptoms fulfilling the inclusion criteria for one of the work packages are asked to participate in the study. Healthy children will be recruited for the general population.

Loss for follow up may occur in the WP II and WP IV. As these children are followed up in the regular outpatient clinic in the same structure loss for follow up we expect to be not higher than 25 %.

Observer bias: the parents will fill in health questionnaires. Investigators performing the measurements are blinded to the clinical data and questionnaire results.

Sequential testing bias: All of the planned measurements will be performed in random order.

Measurement bias: feasibility study has been performed to reduce the measurement bias, tidal breathing with face mask vs single breath with mouthpiece were tested showing comparable results. The mask with the lowest level of plasticizers has been selected [79].

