4.2.1 Primary endpoints

The primary outcome is the molecular composition of tidally exhaled breath as analysed in real-time by SESI-MS.

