5.2 Procedures

(STROBE 5; swissethics 3a) [6,69]

Work package I: 'preschool'

Step 1: recruitment (see 2.4). During the recruitment besides the parent information leaflets and consents, the questionnaire will be distributed to parents. They will be asked to bring the filled-in Luftibus questionnaire on the day of SESI-MS measurement. Asthma risk will be assessed applying the modified asthma predictive index (mAPI) and the Leicester prediction tool to categorise patients to high or low asthma risk groups.

Step 2: measurement visit: All children will undergo a short clinical assessment by the attending physician. Weight and body-length will be measured as per clinical requirements. Information on actual treatment and last medication (if applicable), last food intake will be gathered. Participants will be thoroughly examined for atopic dermatitis during the medical visits, using the SCORing Atopic Dermatitis method (SCORAD), performed by a medical doctor.

All measurements will be performed at the Kinderspital Zurich.

Prior to the measurement, participants will need to have abstained for at least one hour from passive smoking, eating (including chewing gum), beverages (except for plain water), brushing of teeth and using mouthwash. This should cause minimal discomfort, as participants are free to indulge in normal daily activities and dietary habits up to one hour before the beginning of the test session and immediately after its completion.

SESI-MS measurement:

- Children 1.5-4 years of age: for the breath analysis children are comfortably seated on a chair or on the lap of the parent and will be asked to breathe calmly as they usually breathe for about 15 seconds through a sterile mask into the mass spectrometer.
- Infants <1.5 years of age: measurements will be performed while the child is in natural sleep. The child will be in supine position either on the lap of the mother or in the cot. The face mask will be carefully placed over the nose and mouth of the sleeping child. This procedure is entirely risk-free as no alteration of normal breathing is required. After six breath cycles of 15 seconds over a period of several minutes, measurement is complete.

Allergy testing:

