Skin-prick test (SPT) for the 7 most common aeroallergens in Switzerland (*D. pteronissimus*, cat, grass mix, birch, hazelnut, ash, and alder) will be performed in all healthy controls and children with respiratory symptoms \geq 2y whom allergy testing has never been performed before. Results from allergy testing for most of the patients with respiratory symptoms is available routine clinical laboratory testing.

SPT is a simple, safe and quick test, providing results within 15-20 minutes. A drop of the allergen (extract) solution is placed on the skin of child comfortably seated on a chair or on the lap of the parent. The skin is then pricked through the drop using the tip of a lancet – this can feel a little sharp but is not painful and should not bleed. In case of sensitization to an allergen it elicits a small, localised allergic response, in the form of a wheal (bump) and flare (redness) at the site of testing, which disappears within 15 minutes. In the standard procedure local antihistamine gel is applied after the test to avoid itching.

Throat swab

Airway and oral bacteria are metabolically active and may add to the exhaled volatile metabolites. Therefore, airway cultures need to be assessed in all children. Throat swab: a small cotton will be used to swab the posterior nasopharynx and then placed into the culture medium.

Fractional exhaled Nitric oxide (FeNO):

The fraction of exhaled nitric oxide (FeNO) is a non-invasive biomarker associated with airway inflammation and can be measured across all ages in standardized fashion. For the reservoir-offline technique, children are sitting on the legs of the parent or a chair while tidally breathing NO-free air for ten breaths. A reusable inert collection bag is attached to the expiratory side of a non-rebreathing valve

with a resistor in place. Five breaths during relaxed tidal breathing will be sampled, and FeNO will be analysed within 4 hours using a chemiluminescence analyser. FeNO will be assessed in healthy controls only.

The whole procedure will take 40 minutes.

Work package II 'longitudinal':

Step 1: all the subjects from WP I will be asked to continue their participation in WP II. The scheme of the visits will be presented to parents

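### Random test order does not balance what precedes the primary breath sample, because the WP I text gives controls and patients different test batteries

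*Protocol*

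**What the plan says.** Section 4.2.1 defines the endpoint: "The primary outcome is the molecular composition of tidally exhaled breath as analysed in real-time by SESI-MS". Section 5.4 deals with sequential testing bias in one sentence: "All of the planned measurements will be performed in random order". The breath sample is not exempted.

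On who has which test, the protocol says:

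- **FeNO.** Section 5.2, WP I: "FeNO will be assessed in healthy controls only". Section 6.6 repeats this. The WP II and WP III parts of section 5.2 describe FeNO without the restriction.
- **Skin-prick test.** Section 5.2 gives it to all controls and, among patients, to those aged 2 years or more "whom allergy testing has never been performed before". It adds: "Results from allergy testing for most of the patients with respiratory symptoms is available routine clinical laboratory testing". Section 6.6 names controls only.
- **Throat swab.** All children.
- **Spirometry.** From age 4, skipped if done less than two weeks earlier.
- **Breath condensate.** Described for WP II and WP III, not in the WP I procedures.
- **Venous blood.** Section 6.6: patients only, when clinically indicated, at routine visits.

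Other places point the other way. Section 5.3 says that controls have the same regimen as patients, although it then lists tests for controls: "For healthy controls besides the breath test spirometry, exhaled NO measurement and sin-prick test will be performed". The Schedule of Assessments marks FeNO and skin-prick testing without a group split, yet it does label the LuftiBus row as for controls. Section 4.2.2 lists exhaled NO as a secondary endpoint without restriction.

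**The concern.** Randomising the order equalises sequence effects between groups only when every group goes through the same set of tests. If one group has more tests, its breath sample is more often taken after something else, however well the randomisation is done. Here the group with more tests is the healthy controls, so exposure before sampling is tied to case or control status. That is the contrast behind the first WP I question and the asthma against healthy question in WP III.

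If breathing NO-free air, forced exhalation or another preceding test altered any part of the breath signal, the alteration would appear as a healthy against patient difference. Section 7.3 selects m/z peaks with Kruskal-Wallis tests, which compare groups without regard to order. Section 4.3 names only bacterial colonisation and smoke exposure as potential confounders.

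**Working it through.** The protocol gives no figure on this point, so there is none to reproduce.

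**Formulas.** Suppose a child has k other tests in uniformly random order with the breath sample. Then:

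- P(at least one precedes the breath sample) = k/(k+1)
- mean number preceding = k/2
- P(a given test precedes it) = 1/2 if that test is done, 0 if it is not

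A simulation with 100,000 draws per case agreed with the exact values.

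**WP I, age 2 or more** (batteries from section 5.2, WP I)

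| Child | Other tests | k | At least one before | Mean before |
|---|---|---|---|---|
| Control | swab, FeNO, skin-prick | 3 | 3/4 = 75% | 1.5 |
| Patient, already allergy tested | swab | 1 | 1/2 = 50% | 0.5 |
| Patient, never tested | swab, skin-prick | 2 | 2/3 = 67% | 1.0 |

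The share q of patients already tested is described only as most. I assume q from 50% to 100%. The patient average is q × 0.50 + (1 − q) × 0.667:

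- q = 0.5: 0.25 + 0.333 = 58%
- q = 1: 50%

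For single tests:

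- FeNO before the breath sample: 0.5 × 60 = 30 controls expected, against 0 of 120 patients (60 low risk and 60 high risk).
- Skin-prick test before the breath sample: 50% of controls, against (1 − q)/2 = 25% to 0% of patients.

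**WP I, under 2 years.** If the age limit on skin-prick testing also covers controls, controls have swab and FeNO (k = 2, 67%) and patients have the swab (k = 1, 50%).

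**Same-visit blood draw in WP I patients, counted as one more test in the sequence.** An already tested patient rises to k = 2, 67%. A never-tested patient rises to k = 3, 75%. If every patient had one, the average for q from 0.5 to 1 would be 0.5 × 0.667 + 0.5 × 0.75 = 71%, down to 67%, against 75% in controls.

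**WP III**

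| Child | Other tests | k | At least one before |
|---|---|---|---|
| Control | swab, FeNO, skin-prick, spirometry, condensate | 5 | 5/6 = 83% |
| Allergy-tested patient, FeNO in all (section 5.2) | swab, FeNO, spirometry, condensate | 4 | 4/5 = 80% |
| Same, FeNO in controls only (section 6.6) | swab, spirometry, condensate | 3 | 3/4 = 75% |
| Same, and spirometry skipped as recent | swab, condensate | 2 | 2/3 = 67% |

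**Identical batteries (section 5.3 taken literally).** k is the same in both groups and the difference is 0.

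**Breath sample first in every child.** P(any other study test precedes it) is 0% in both groups, whatever the batteries.

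**The case against.** The strongest reply is that the premise rests on one side of an internal contradiction. Section 5.3 promises the same regimen and the Schedule of Assessments shows no split; on that reading nothing is imbalanced. This stands as a limit on the point. It does not remove it, because the specific procedure text in section 5.2 (WP I) and section 6.6 says otherwise, and staff carrying out the visit would follow that text.

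Other replies also narrow the point. The skin-prick age limit and patient-only blood draws reduce the WP I gap; a never-tested patient with a same-visit draw equals the controls. On section 5.2's own text, the WP III gap is only 83% against 80%. Questions that compare patients with patients, such as protracted bacterial bronchitis or later asthma against transient wheeze, are not shown to be affected.

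A reader might infer two stronger things that the protocol does not support.

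- **That the primary outcome is biased.** The percentages describe order, not carry-over. The low-plasticizer mask and the one-hour abstention show care about the sampling device and oral intake. They do not show that swabbing, NO-free breathing or a skin gel ("In the standard procedure local antihistamine gel is applied after the test to avoid itching") changes SESI-MS peaks.
- **That random order cannot work in infants.** For children under 1.5 years, section 5.2 says that "measurements will be performed while the child is in natural sleep". That sets a condition for the breath sample but no place in the sequence. The same constraint applies to a breath-first rule.

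**Conclusion.** The point holds as a design weakness that is cheap to remove, mainly in WP I. With the batteries in the WP I procedures, random order leaves at least one other study test before SESI-MS in 75% of controls against 50% to 58% of patients from age 2. Under age 2 it is 67% against 50% if the age limit covers controls. FeNO comes first in about half of controls and in no patient. In WP III the gap runs from 3 to 16 percentage points (83% against 80% down to 67%), depending on which section governs FeNO and whether spirometry is skipped.

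These figures assume uniformly random order, the group-specific text rather than section 5.3, an already-tested share of 50% to 100%, and no same-visit blood draw or other clinic tests that day. The imbalance concerns healthy against patient contrasts only. Its effect on the breath signal cannot be sized from the protocol and may be nil.

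**What to change.** - In sections 5.4 and 5.2, state that SESI-MS is the first study measurement in every child and that the remaining tests follow in random or fixed order.
- Where this is not possible, record the order and the time since any earlier test.
- Reconcile the Schedule of Assessments and sections 5.2, 5.3 and 6.6 on who has FeNO and skin-prick testing.

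The first change protects the primary outcome whichever reading of the batteries is confirmed. It adds no procedure. The cost is protocol wording and some visit planning, mainly for infants measured in natural sleep, whose other tests would have to wait until the breath sample is done.

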6. PROJECT POPULATION

(STROBE 6; HRO Annex 2/1.2) [4,6]

As our study approach is exploratory, thus the possibilities for sample size estimation are limited.

WP I 'preschool': 180 preschool children aged 6 months to 4 years will be included in WP 1.

Three groups will be investigated:

- 60 Healthy controls
- 60 Patients with chronic respiratory symptoms (wheezing, cough) and low risk for asthma
- 60Patients with chronic respiratory symptoms (wheezing, cough) and high risk for asthma

WP II 'longitudinal'; prospective longitudinal observational cohort study: For prospective assessment of health outcomes parents of the participants of WP I will be asked to take part in longitudinal follow-up study. Participants will be followed until reaching the age where lung function testing reliably can be conducted (six years). Therefore, the duration of the follow depends on the age at study entry (two to six years). Two follow-up schemes will be offered:

This scheme consists of one follow-up visit at the age six. We aim for a participation of rate 75% (n=135) of the WP I population.

- 45 healthy controls
- 45 patients with chronic respiratory symptoms (wheezing, cough) and low risk for asthma
- 45 patients with chronic respiratory symptoms (wheezing, cough) and high risk for asthma

WP III 'school-age'; prospective cross-sectional exploratory observational matched case control study:

In this case-control study we enrol three groups with sex- and age-matched school-aged children (age 5 - 18 years):

- 30 healthy controls
- 30 children with known allergic asthma
- 30 children with known non-allergic asthma

WP IV: 'school-age' assessment during asthma worsening.

Patients from WP III will be asked to return for two additional visits in the case of an asthma worsening. Visit Ex1 will be done within 1 week of start of asthma worsening and Visit Ex2 one month after asthma worsening is resolved. Patients with the need of an acute treatment with systemic corticosteroids or hospitalization will not be included in this part.

We aim to include 10-15 asthmatic patients from WP III

6.1 Inclusion criteria

All WP:

- informed consent by parents (and by children if age > 8 years)
- active/passive understanding of German or other languages spoken in Switzerland
- No chronic respiratory symptoms or diseases in healthy controls

WP I and II:

All groups:

• age 6 months -4 years

Wheeze group:

• preschool wheeze (more than two episodes of wheeze during 12 months prior to inclusion) Cough group:

• daily cough for at least 4 weeks prior to inclusion

WP III:

All groups:

• age 5 years - < 18 years

Asthma group:

• doctor diagnosed asthma (according to current guidelines)

6.2 Exclusion criteria

II WP:

- heart failure diagnosed after birth affecting pulmonary circulation
- specific respiratory diseases: cystic fibrosis; primary ciliary dyskinesia; interstitial lung disease; airway malformation
- any disability that prevents proper execution of any measurement manoeuvre (breath analysis, spirometry)
- fever of at least 38.5°C during the last two weeks prior to the planned first visit

WP III/IV:

Asthma group:

• uncontrolled asthma (assessed by ACQ) requiring oral corticosteroids

6.3 Criteria for withdrawal / discontinuation of participants

Patients need to discontinue from the project in the case of withdrawal of informed consent or if families move to another country. The person who is responsible for anonymization of the data will find and prohibit the data from further analysis.

In case if a healthy control develops chronic respiratory symptoms during the period of longitudinal control, the subject will be withdrawn from the group of healthy controls and in case of fulfilling the criteria of one of the study groups will be offered to continue the follow up as a child with respiratory symptoms.

PROJECT ASSESSMENTS

(STROBE 7; HRO Annex 2/1.2) [4,6]

Describe procedures, measurements, collection, storage of samples taken, data storage, etc.

6.4 **Project flow chart(s) / table of procedures and assessments**

See above the schedule of assessment (FLOW OF RESEARCH PROJECT).

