2.4 Participant Information and Informed Consent

(HRO Art. 8, Annex 2/1.3-1.5) [4]

Participants will be informed about the research project (see below) and consent is sought from each participant. Informed consent will be sought for general and further use of data and/or biological samples.

A) Children with respiratory symptoms:

Parents and patients will be directly informed by the treating physician during clinical visits. Recruitment will be done by the PI, the Co-PI or the research assistants (see staff list). After thorough oral information, informed written consent (IC) about the research project will be obtained from all parents or legal guardians and children older than 14 years who have volunteered to take part in the study. IC will be obtained without delay during the study visit before any study related actions are taken.

B) Healthy controls:

Patients will be recruited from the public and day nurseries. Information by flyers and letters to schools and day care center's (Document Begleitbrief_Schule_gesunde Kontrollen_v1_12.02.2017. Interested parents will contact the study team via the telephone number provided, where they will receive detailed information. At the study date after thorough oral information, informed written consent (IC) about the research project will be obtained from all parents or legal guardians and children older than 14 years who have volunteered to take part in the study. IC will be obtained without delay during the study visit before any study related actions are taken.

Participants will not receive any financial compensation. Travel expenses will be reimbursed on request. As small present will be given to participating children (participation diploma, a small toy and/or a little bag with sweets)

Rationale to include particularly vulnerable participants:

We aim to identify and validate the most specific metabolites in exhaled air to reliably and non-invasively diagnose both early infection and inflammation processes in the lungs of children with respiratory symptoms. This will help to understand the early pathologic processes of the disease.

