5.1 Type of research and general project design (STROBE 4)

Type: observational

Single center

Design:	
WP 1 / WP III	Cross sectional case control study
WPII	Longitudinal cohort study
WP IV	longitudinal assessment of asthma worsening

Our project will consist of four work packages (WP):

WP I 'preschool'; prospective cross-sectional exploratory observational matched case control study:

WP I will consist of age and sex matched case-control study including 180 preschool children aged 6 months to 4 years. It is designed for phenotyping children with chronic respiratory symptoms by SESI-MS.

Three groups will be investigated:

Healthy controls (n=60) and two groups cases stratified by diagnostic certainty: A) patients with chronic respiratory symptoms (wheezing, cough) and low risk for asthma (n=60) and B) patients with chronic respiratory symptoms (wheezing, cough) and high risk for asthma (n=60).

Asthma risk will be assessed applying the modified asthma predictive index (mAPI) and the Leicester prediction tool [14,66].

WP II 'longitudinal'; prospective longitudinal observational cohort study: For prospective assessment of health outcomes parents of the participants of WP I will be asked to take part in longitudinal follow-up study. Participants will be followed until reaching the age where lung function testing reliably can be conducted (six years). Therefore, the duration of the follow depends on the age at study entry (two to six years). Two follow-up schemes will be offered:

- 1. This scheme consists of one follow-up visit at the age six. We aim for a participation of rate 75% (n=135) of the WP I population.
- 2. For this scheme parents will be offered yearly follow-up visits until the age of six. We aim to recruit at least 45 healthy controls, 45 patients with chronic respiratory symptoms (wheezing, cough) and low risk for asthma, and 45 patients with chronic respiratory symptoms (wheezing, cough) and high risk for asthma

WP III 'school-age'; prospective cross-sectional exploratory observational matched case control study: In this case-control study we enrol three groups with sex- and age-matched school-aged children (age 5 - 18 years): A) healthy controls (n=30), B) children with known allergic asthma (n=30) and C) children with known non-allergic asthma (n=30).

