7. STATISTICAL METHODOLOGY

7.1 Determination of Sample Size

(STROBE 10) [6]

Traditional methods for estimating sample sizes needed to detect a minimum meaningful difference cannot be applied to our exploratory pilot design. Tentative estimations can be made based on sample size requirements for factor analysis [73]: Assuming a variable-to-factor ratio of at least seven, the minimum necessary sample size for good (92%) model agreement is 55 to 80. Calculations for proteomic profiling using MS [74] suggest a similar range of sample sizes. Based on our prior experience of exploratory breath analysis [52, 55] we aim to recruit at least 60 patients with chronic respiratory symptoms with high risk for asthma, 60 patients with chronic respiratory symptoms with low risk for asthma and 60 healthy controls for WP I. We assume that we can recruit 75% of the original population to WP III, 30 allergic asthma patients, 30 no allergic asthma patients and 30 healthy controls for WP II.

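### Section 6.3 bars data from further analysis after a family's move abroad as it does after withdrawal of consent, which excludes measurements already validly made

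*Protocol*

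**What the plan says.** Section 6.3 names the two triggers together: "Patients need to discontinue from the project in the case of withdrawal of informed consent or if families move to another country". It continues directly: "The person who is responsible for anonymization of the data will find and prohibit the data from further analysis". That second sentence does not say which trigger it applies to, or whether it covers only data collected after the event.

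Other sections that bear on the point:

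- Section 2.4, on consent: "Informed consent will be sought for general and further use of data and/or biological samples".
- Section 5.1, on WP I: "WP I will consist of age and sex matched case-control study including 180 preschool children aged 6 months to 4 years". WP I and WP III are described there as cross-sectional. Under section 5.2, risk group and breathprint in WP I come from recruitment and one measurement visit.
- Section 5.1 also says that WP II follows WP I children to age six, for two to six years depending on age at entry. Section 6 sets the target: "We aim for a participation of rate 75% (n=135) of the WP I population".
- Section 5.4, on WP II and WP IV: "loss for follow up we expect to be not higher than 25" percent.
- Section 7.3.2 provides for recruiting further patients and controls to make up for missing data and drop-outs on the primary outcome. It does not say what happens to data already collected from a child who drops out.
- The synopsis schedules WP I and WP III for 03/18 to 08/2020, and WP II for 03/18 to 08/2022.

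No section says that data collected before a move abroad are kept.

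**The concern.** The two triggers call for different handling. Withdrawal of consent concerns permission to use the data. A move abroad concerns only whether the child can attend further visits. Section 6.3 gives both the same consequence for the data.

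The WP I and WP III measurements are complete when the visit ends, and a later move cannot make them less valid. Under 6.3 as written, whether a child counts in a cross-sectional comparison would depend on a later event unrelated to consent or data quality. Two things are at stake:

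- **Precision.** Usable breathprints and WP II visits already made are set aside.
- **Description of attrition.** Section 5.4 expects losses of up to a quarter in WP II. Judging whether the children lost resemble those retained requires the baseline data of those lost, and the rule withholds exactly those data for children who move.

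**Working it through.** **1. What the rule does to each kind of data when a family moves abroad**

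| Data | Complete before the move? | Affected by the move? | Under 6.3 as written |
|---|---|---|---|
| WP I breathprint and risk group | Yes | No | Barred from later analyses |
| WP III breathprint and asthma group | Yes | No | Barred from later analyses |
| WP II visits already made | Yes | No | Barred from later analyses |
| WP II or WP IV visits not yet made | No | Yes, cannot be collected | Not available in any case |

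Only the last row is a real consequence of moving. The first three arise from the wording.

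**2. The plan's own figures**

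WP I has 3 × 60 = 180 children. At 75% participation, 0.75 × 180 = 135 and 0.75 × 60 = 45 per group. Both match the protocol.

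**3. Illustration of size**

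The protocol gives no rate of moves abroad, so the rates r = 1%, 3% and 5% per year are assumptions. So is the 3-year average exposure, which lies within the stated two to six years. The base is the 135 children expected in WP II, since they are the ones still in the project after the WP I visit.

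Expected number barred = 135 × [1 − (1 − r)³]:

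- r = 1%: 135 × 0.0297 = 4.0
- r = 3%: 135 × 0.0873 = 11.8
- r = 5%: 135 × 0.1426 = 19.3

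**4. If WP I is analysed soon after 08/2020**

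Moves after the analysis would then not matter for WP I. WP I runs for about 2.5 years, so the average time from measurement to its end is about 1.25 years, assuming even recruitment. Expected number = 135 × [1 − (1 − r)^1.25]:

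- r = 1%: 1.7
- r = 3%: 5.0
- r = 5%: 8.4

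**5. Against the sample-size basis**

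Section 7.1 says that "the minimum necessary sample size for good (92%) model agreement is 55 to 80". Without replacement, a group of 60 falls below 55 once more than 5 of its children are barred (5/60 = 8.3%).

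**6. With data up to the move retained**

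WP I stays at 180 whatever the rate of moves.

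**The case against.** The strongest reply is that the sentence is loosely drafted rather than a deliberate rule. The data bar may have been meant for withdrawal of consent only, and the word *further* may leave completed analyses untouched. Both readings are possible, but the text supports the first nowhere. The second reduces the loss for WP I without removing it, and it does not help WP II. A one-clause clarification is needed on either reading.

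Section 7.3.2 is a real mitigation: drop-outs on the primary outcome are to be replaced. That can hold numbers up while recruitment is open. On the synopsis schedule, however, WP I and WP III close in 08/2020 and WP II runs two years longer. Replacement also returns neither the barred data nor the baseline of the children lost.

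A reader might infer more than the protocol supports:

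- *The data are deleted.* Section 6.3 bars further analysis and does not order deletion.
- *WP I has no margin.* Section 7.1 aims for at least 60 per group, and section 7.3.2 allows replacement.
- *Matched sets collapse.* Groups are matched on age and sex, but no matched sets are defined, and section 7.3 plans independent-sample and Kruskal-Wallis tests. Losing one child does not disqualify others.
- *The loss is differential between cases and controls.* This is possible but not shown. Section 5.3 first seeks controls among classmates, groupmates and siblings of patients, and siblings would normally move with the patient.
- *Up to about 26 children are lost.* That figure applies 3 years at 5% to all 180 (180 × 0.1426 = 25.7), although only 135 are expected to continue.

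**Conclusion.** The point holds as a defect in the wording of a stated rule. Section 6.3 attaches a bar on further analysis to a move abroad, with no reason in consent or data quality, and nothing elsewhere in the protocol lifts it. It reaches WP I and WP III breathprints already taken and WP II visits already made, for any analysis done after the move.

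The size is unknown. Under the assumed rates of 1% to 5% per year it is about 4 to 19 of the 135 children expected in WP II over 3 years, or about 2 to 8 for a WP I analysis soon after 08/2020. The defect does not depend on these figures, and any loss from this source is avoidable. The wording should be corrected, but it does not by itself undermine the study.

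**What to change.** In section 6.3:

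- Limit the prohibition on further analysis to withdrawal of consent, applied as the consent form provides.
- State that when a family moves abroad, study visits end, the child counts as lost to follow-up in WP II or WP IV, and all data collected up to the move stay in the WP I, WP II and WP III analyses.

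The cost is about one sentence, with no new visits or participants. Section 2.4 says only that consent for further use will be sought, and the consent form is not among the documents at hand. The new wording should therefore be checked against that form before it is adopted.
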